### **10.3 Informed Consent Process**

Informed consent is required for all patients participating in this study. The patient signs one informed consent for both the Double-blind Phase and the Open-label Extension Phase of the study. In obtaining and documenting informed consent, the Investigator must comply with applicable regulatory requirements and must adhere to GCP regulations. It is the responsibility of the Investigator to ensure that written informed consent is obtained from the patient before any activity or procedure is undertaken that is not part of routine care.

Informed consent is a process that is initiated prior to the individual's agreeing to participate in the study and that continues throughout the individual's study participation. The Investigator or designee will discuss extensively with the participant patient the study risks. Copies of the current, IRB/IEC-approved ICF detailing the risks and benefits of study participation will be provided to the participants. Consent forms describing in detail the study drug and study procedures/intervention and risks will be fully explained to the patient and written documentation of informed consent will be required prior to starting participation in the study. Upon reviewing the document, the Investigator or designee will explain the research study to the participant and answer any questions that may arise. The participants will sign the ICF prior to any procedures being performed specifically for the study. The participants should have sufficient opportunity to discuss the study and process the information in the consent process prior to agreeing to participate. The participants may withdraw consent at any time throughout the course of the study. A signed copy of the ICF will be given to the participants for their records. Participants must be re-consented to the most current version of the ICF during their participation in the study.

### **10.4 Patient Confidentiality**

In order to maintain patient privacy, all eCRFs, study drug accountability records, study reports, and communications will identify the patient by assigned patient number. The Investigator will grant monitor(s) and auditor(s) from the Sponsor or its designee and regulatory authority(ies) access to the patient's original medical records for verification of data gathered on the eCRFs and to audit the data collection process. The patient's confidentiality will be maintained and will not be made publicly available to the extent permitted by the applicable laws and regulations.

Participant confidentiality is strictly held in trust by the participating Investigators, their staff, and the Sponsor(s) and their agents. This confidentiality is extended to cover testing of biological samples and genetic tests in addition to the clinical information relating to participating patients.

The study protocol, documentation, data, and all other information generated will be held in strict confidence. No information concerning the study or the data will be released to any unauthorized third party without prior written approval of the Sponsor.

The study monitor or other authorized representatives of the Sponsor may inspect all documents and records required to be maintained by the Investigator, including, but not limited to, medical records (office, clinic, or hospital) and pharmacy records for the participants in this study.

---

## **11.0 Data Handling and Quality Assurance**

All participant data relating to the study will be recorded on eCRFs unless transmitted to the Sponsor or designee electronically (eg, laboratory data). No data are to be recorded directly in the eCRFs (eg, all data will have a unique source). The Investigator is responsible for verifying that data entries are accurate and correct by physically or electronically signing the eCRF.

The Investigator must maintain accurate documentation (source data) that supports the information entered in the eCRF.

The Investigator must permit study-related monitoring, audits, IRB/IEC review, and regulatory agency inspections and provide direct access to source data documents.

The Sponsor or designee is responsible for the data management of this study, including quality checking of the data.

Study monitors will perform ongoing source data verification to confirm that data entered into the eCRF by authorized site personnel are accurate, complete, and verifiable from source documents; that the safety and rights of participants are being protected; and that the study is being conducted in accordance with the currently approved protocol and any other study agreements, ICH-GCP, and all applicable regulatory requirements.

Records and documents, including signed ICFs, pertaining to the conduct of this study must be retained by the Investigator for 2 years after the marketing approval of the study drug or after discontinuing clinical development unless local regulations or institutional policies require a longer retention period. No records may be destroyed during the retention period without the written approval of the Sponsor. No records may be transferred to another location or party without written notification to the Sponsor. If the Investigator withdraws from the responsibility of keeping the study records, custody must be transferred to a person willing to accept the responsibility. If a custodial change or a change in record location occurs, the Sponsor must be notified in writing.

---

## **12.0 Administrative Procedures**

### **12.1 Protocol Adherence**

It is vital to the success of the study that the Investigator adhere to the details of the protocol, and thus to keep to a minimum the number of cases later classified as “incomplete,” “unusable,” or “not evaluable.” If, in the interest of safety and/or well-being of a particular patient, it is necessary to depart from the protocol, then that protocol deviation will pertain to that individual patient only and will be documented. Protocol deviations due to lack of patient compliance must also be documented.

The site monitor will review protocol deviations throughout the course of monitoring visits and document new findings of deviations. The monitor will notify the Investigators of deviations verbally or in writing. The IRB/IEC should be notified of all protocol deviations in a timely manner according to IRB/IEC requirements.

### **12.2 Publication of Study Findings**

All information regarding CR845 provided by Sponsor to the Investigator is privileged and confidential information. By conducting this study, the Investigator affirms to the Sponsor that he/she will maintain, in strict confidence, information furnished by the Sponsor, including data generated from this study, except as exempted for regulatory purposes. All data generated during the conduct of this study are owned by Sponsor. The Investigator agrees to use the information to conduct the study and will not use it for other purposes without written permission from Sponsor. Partial or full data or results from this study cannot be published without express written consent from Sponsor. It is understood that there is an obligation to provide Sponsor with complete data obtained during the study. The information obtained from the clinical study will be used toward the development of CR845 and may be disclosed to regulatory authority, other Investigators, corporate partners, or consultants, as required.

---

## 14.0 Appendix

### 14.1 Appendix 1: New York Heart Association Classification of Heart Failure

#### New York Heart Association (NYHA) Classification of Heart Failure

Class	Patient Symptoms
Class I (Mild)	No limitation of physical activity. Ordinary physical activity does not cause undue fatigue, rapid/irregular heartbeat (palpitation) or shortness of breath (dyspnea).
Class II (Mild)	Slight limitation of physical activity. Comfortable at rest, but ordinary physical activity results in fatigue, rapid/irregular heartbeat (palpitation) or shortness of breath (dyspnea).
Class III (Moderate)	Marked limitation of physical activity. Comfortable at rest, but less than ordinary activity causes fatigue, rapid/irregular heartbeat (palpitation) or shortness of breath (dyspnea).
Class IV (Severe)	Unable to carry out any physical activity without discomfort. Symptoms of fatigue, rapid/irregular heartbeat (palpitation) or shortness of breath (dyspnea) are present at rest. If any physical activity is undertaken, discomfort increases.

[[Criteria Committee of the New York Heart Association 1994](#)]

**14.2 Appendix 2: Worst Itching Intensity Numerical Rating Scale (NRS)**

This is a representation of the content of the instrument to be used. Please refer to the Study Reference Manual for the instrument to be administered to patients and instructions.

**Completed in Dialysis Unit or at Home?** (please mark only one)

**Dialysis Unit**

**Home**

**INSTRUCTIONS**

Please indicate the intensity of the **WORST ITCHING** you experienced over the past 24 hours by marking the box with the number that best describes it. After completing the scale below, please provide your initials in the **SUBJECT INITIALS** box indicating that you completed the scale by yourself and the **DATE** and **TIME** you completed the scale.

**Worst Itching Over the Past 24 Hours**

Please indicate the intensity of the **WORST ITCHING** you experienced over the past 24 hours.

0	1	2	3	4	5	6	7	8	9	10
										
NO ITCHING					WORST ITCHING IMAGINABLE					

**Date Completed:**

									
D	D	M	M	M	Y	Y	Y	Y	Y

**Time:**

		:		
	AM		PM	

**SUBJECT INITIALS**

First	Middle	Last
		

**14.3 Appendix 3: Skindex-10 Scale**

This is a representation of the content of the instrument to be used. Please refer to the Study Reference Manual for the instrument to be administered to patients and instructions.

INSTRUCTIONS: During the past WEEK , how often have you been bothered by:							
	0 (Never bothered)	1	2	3	4	5	6 (Always bothered)
1. Your itching							
2. The persistence/reoccurrence of your itching							
3. The appearance of your skin from scratching							
4. Frustration about your itching							
5. Being annoyed about your itching							
6. Feeling depressed about your itching							
7. Feeling embarrassed about your itching							
8. The effects of your itching on your interactions with others (for example: interactions with family, friends, close relationships, etc.)							
9. The effects of your itching on your desire to be with people							
10. The effect of your itching making it hard to work or do what you enjoy							

**Date Completed:**

							
D	D	M	M	M	2	0	
		Y	Y	Y	Y		

**Time:**

		:		
	AM		PM	

**SUBJECT INITIALS**

First	Middle	Last
		

**14.4 Appendix 4: 5-D Itch Scale**

This is a representation of the content of the instrument to be used. Please refer to the Study Reference Manual for the instrument to be administered to patients and instructions.

1.	DURATION:	During the last 2 weeks, how many hours a day have you been itching?						
		Less than 6 hrs/day	6-12 hrs/day	12-18 hrs/day	18-23 hrs/day	All day		
								
2.	DEGREE:	Please rate the intensity of your itching over the past 2 weeks						
		Not present	Mild	Moderate	Severe	Unbearable		
								
3.	DIRECTION:	Over the past 2 weeks has your itching gotten better or worse compared to the previous month?						
		Completely resolved	Much better, but still present	Little bit better, but still present	Unchanged	Getting Worse		
								
4.	DISABILITY:	Rate the impact of your itching on the following activities over the last 2 weeks						
		Sleep	Never affects sleep	Occasionally delays falling asleep	Frequently delays falling asleep	Delays falling asleep and occasionally wakes me up at night	Delays falling asleep and frequently wakes me up at night	
								
			N/A	Never affects this activity	Rarely affects this activity	Occasionally affects this activity	Frequently affects this activity	Always affects this activity
		Leisure/Social						
		Housework/Errands						
		Work/School						

5. DISTRIBUTION:	Mark whether itching has been present in the following parts of your body over the last 2 weeks. If a body part is not listed, choose the one that is closest anatomically.			
	Head/Scalp		Soles	
	Face		Palms	
	Chest		Tops of Hands/Fingers	
	Abdomen		Forearms	
	Back		Upper Arms	
	Buttocks		Points of Contact w/ Clothing (e.g waistband, undergarment)	
	Thighs			
	Lower legs		Groin	
	Tops of Feet/Toes			

Date Completed:										
					2	0				
D	D	M	M	M	Y	Y	Y	Y	Y	Y

Time:			
		:	
 AM	 PM		

SUBJECT INITIALS		
First	Middle	Last

**14.5 Appendix 5: Patient Global Impression of Change**

This is a representation of the content of the instrument to be used. Please refer to the Study Reference Manual for the instrument to be administered to patients and instructions.

**Since the start of the study, my itch is:**

- 1.  Very much improved
- 2.  Much improved
- 3.  Minimally improved
- 4.  Not changed
- 5.  Minimally worse
- 6.  Much worse
- 7.  Very much worse

Date Completed:							
					2	0	
D	D	M	M	M	Y	Y	Y

Time:			
		:	
	AM		PM

SUBJECT INITIALS		
First	Middle	Last

---

## 14.6 Statistical Appendix

This appendix provides further details related to the treatment of missing data for the primary and sensitivity analyses of the primary endpoint.

For multiple imputations and other instances where random seeds are required, the values used (in order) are:

8392857  
2985729  
1843255  
9086284  
5547484  
8017456  
9597295  
2252256  
4821871  
9852467  
5126715  
3232132  
9841654  
3645284  
1587345

Note that not all seeds may be required in programming the multiple imputations. If additional seeds are needed, they will be chosen by adding 1 to each of the values above, again using them in order.

The number of imputations for the multiple imputations will be 20.

For the primary analysis, a multi-stage process will be applied:

Stage 1: Subjects will have their 11-point NRS scores imputed. First, using all visits, intermittent missing data will be imputed using the Markov Chain Monte Carlo (MCMC) method implemented with the SAS MI procedure; data imputed following subject discontinuation via this process will be censored out of the resulting dataset so that only intermittent missing data is imputed via this method. Second, monotone missing data will be imputed following subject discontinuation using SAS proc MI. For each stage, MI will be performed within treatment group with covariates for baseline NRS score, use of prior anti-itch medication, and presence of select medical conditions. Should convergence issues occur due to small cell size for the one or both of the categorical covariates at either stage, the appropriate covariate(s) will be removed from the model.

Stage 2: Using the resulting complete datasets, the change from baseline with respect to the 11-point NRS will be calculated; patients will be categorized as responder if they have a 3-point (or greater) improvement over baseline. Week 12 values will serve as the primary timepoint. The 20 MI runs will be analyzed independently using a logistic

---

model and the results combined using SAS proc MIANALYZE. Logistic model covariates will include treatment, baseline NRS score, use of prior anti-itch medication, and presence of select medical conditions. As with the MI, should convergence issues occur due to small cell sizes, the appropriate categorical covariate(s) will be dropped as necessary.

Should a sample size increase occur, the above process will be implemented completely independently among subjects contributing the interim results and those following the interim analysis.

For the tipping point analysis, a shift parameter will be applied to only subjects in the active group, running from 0 to 5 points in 0.25-point increments or until the conclusions of the analysis “tip” and the results are no longer significant. This analysis will not be performed should the initial primary results fail to achieve significance.

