### 8.2 Determination of Sample Size

The planned sample size for this study is 350 (175 per treatment group) male and female hemodialysis patients with chronic moderate-to-severe pruritus (mean baseline 24-hour Worst Itching Intensity NRS score  $\geq 5$ ), randomized at approximately 95 clinical sites. The sample size may be increased to 500 patients (250 per treatment group) based on the results of a planned unblinded interim assessment conducted when approximately 50% of the planned 350 first patients have been randomized and have either completed the 12-week Double-blind Treatment Period or have discontinued from double-blind treatment early. The planned interim assessment will be conducted by an Independent Data Monitoring Committee (IDMC). Details related to the sample size re-estimation are included in [Section 8.4.1](#).

The sample size calculation is based on results of a completed Phase 2 double-blind, placebo-controlled study (CR845-CLIN2101) of CR845 in hemodialysis patients who had moderate-to-severe pruritus. In this study, approximately 30% of patients randomized to the placebo group reported  $\geq 3$ -point improvement from baseline with respect to the 24-hour Worst Itching Intensity NRS at the end of treatment (Week 8). The proportion of patients who received CR845 and reported a similar improvement in itch scores ranged from approximately 60% to 45% (ie, 30% to 15% difference from

placebo), depending on the dose of active study drug (0.5 mcg/kg, 1.0 mcg/kg, 1.5 mcg/kg).

Given a sample size of 350 patients (175 per treatment group) and assuming a true response rate of 30% for the placebo group and a true response rate of 50% for the CR845 group (defining response as an improvement from baseline  $\geq 3$  points with respect to the Worst Itching Intensity NRS at Week 12), a 2-sided continuity corrected Chi-square will have 96% power to detect a treatment difference. The power of this test statistic would be  $\geq 84\%$  for differences from placebo as low as 0.16 (Table 4).

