### **8.7.3 Hypothesis Testing Strategy**

The efficacy of CR845 0.5 mcg/kg compared to placebo in pivotal Phase 3 study CLIN3103 will be evaluated based on 1 primary and 7 secondary efficacy endpoints.

Testing of the primary efficacy endpoint will be 2-sided and conducted at the 5% error level. The study will be considered positive if the null hypothesis of no treatment difference in the primary efficacy analysis of the primary endpoint (proportion of patients achieving  $\geq 3$ -point improvement from baseline with respect to the Worst Itching Intensity NRS) is rejected in favor of the alternative that patients randomized to CR845 experience significantly less itching compared to patients randomized to placebo.

To protect the Type 1 error, a gate-keeping strategy will be implemented. Although the p values corresponding to the hypothesis testing of the secondary variables will be reported, they will only be considered inferential if the primary analysis is statistically significant. Testing of the secondary efficacy endpoints will be performed sequentially at a 2-sided 5% error level in the order specified below. If the test of an endpoint in the sequence is not statistically significant, the p-value for the tests corresponding to the remaining endpoints in the sequence will not be considered inferential and the null hypotheses for the subsequent tests will not be rejected.

- Proportion of patients achieving  $\geq 4$ -point improvement from baseline with respect to the weekly mean of the daily 24-hour Worst Itching Intensity NRS at Week 12 of the Double-blind Treatment Period;
- Proportion of patients achieving  $\geq 3$ -point improvement from baseline with respect to the weekly mean of the daily 24-hour Worst Itching Intensity NRS at Week 8 of the Double-blind Treatment Period;
- Proportion of patients achieving  $\geq 3$ -point improvement from baseline with respect to the weekly mean of the daily 24-hour Worst Itching Intensity NRS at Week 4 of the Double-blind Treatment Period;
- Proportion of patients achieving  $\geq 4$ -point improvement from baseline with respect to the weekly mean of the daily 24-hour Worst Itching Intensity NRS at Week 8 of the Double-blind Treatment Period;
- Proportion of patients achieving  $\geq 4$ -point improvement from baseline with respect to the weekly mean of the daily 24-hour Worst Itching Intensity NRS at Week 4 of the Double-blind Treatment Period;

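### Twenty imputations leave avoidable seed-dependent noise in the primary p-value: the test stays valid, but a result close to 0.05 could be decided by the seed list

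*Protocol*

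**What the plan says.** Protocol Section 14.6 covers missing data in the primary and sensitivity analyses of the primary endpoint. It fixes one number: "The number of imputations for the multiple imputations will be 20". Each completed dataset is analysed with a logistic "model and the results combined using SAS proc MIANALYZE".

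The seeds are also fixed: "For multiple imputations and other instances where random seeds are required, the values used (in order) are", followed by fifteen values. For any further seeds the rule is: "If additional seeds are needed, they will be chosen by adding 1 to each of the values above, again using them in order".

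Section 8.7.3 sets the decision rule: "Testing of the primary efficacy endpoint will be 2-sided and conducted at the 5% error level". The seven secondary endpoints are tested inferentially only if the primary test succeeds.

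In the tipping-point analysis (Sections 8.7.1 and 14.6), a shift is applied to the active arm in 0.25-point steps from 0 to 5 points "or until the conclusions of the analysis" change, meaning that p passes 0.05.

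The protocol gives no reason for choosing 20, no criterion for Monte Carlo error, no rule for raising the number, and no expected rate of missing data.

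**The concern.** A multiple-imputation p-value is partly random: the same patients analysed with another seed list give a slightly different answer. Fixing the seeds makes the answer reproducible, but it remains one draw from the distribution of answers that those patients could have produced. The spread shrinks with the square root of the number of imputations.

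Whether the study is positive, and whether the secondary sequence opens, turns on one cut at 0.05. If the result falls close to that cut, an arbitrary list of integers could settle it, and a later reader could rerun the analysis with other seeds and dispute it. The tipping-point analysis is exposed for a further reason: it is read at the shift where p crosses 0.05, which is where small noise matters most.

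**Working it through.** **The plan's own figures.** These do not depend on the number of imputations, but they confirm the design inputs. With 175 per arm, "assuming a true response rate of 30% for the placebo group and a true response rate of 50% for the CR845 group", and a continuity-corrected chi-square test, Table 4 recomputes as 96.3%, 92.0%, 84.8% and 79.9% (stated: 96%, 92%, 84%, 79%). Table 5 recomputes exactly as 134, 164, 204, 230 and 262. The protocol states no figure for Monte Carlo error.

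**Inputs.** From the protocol: m = 20 imputations and a two-sided 0.05 level. Assumed: a fraction of missing information g of 3% to 20%. In a patient-level simulation (175 per arm, 12 weekly means, monotone regression imputation within arm, logistic model), discontinuation of 5%, 10%, 15%, 20% and 30% gave a mean g of about 3%, 8%, 10%, 14% and 16%.

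**Model.** Scale the total variance to 1, so the within-imputation variance is 1 − g and the between-imputation variance is g. Let z be the statistic with unlimited imputations. Over repeated seed sets:

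- pooled estimate Q ~ Normal(z, g/m)
- estimated between-imputation variance B = g × χ²(m−1)/(m−1)
- total variance T = (1 − g) + (1 + 1/m)B
- p from Q/√T on a t distribution with (m − 1)(1 + 1/r)² degrees of freedom, where r = (1 + 1/m)B/(1 − g)

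**Check by hand.** At g = 10% and m = 20, √(0.10/20) = 0.071. Estimating B raises the SD of the pooled statistic to about 0.079. A z of 2.1 lies 2.10 − 1.96 = 0.14 above the cut, and 0.14/0.079 ≈ 1.8 SD, which leaves about 4% in the tail. Simulation with the full rules gives 4.6%.

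**Share of seed sets reporting p > 0.05 with m = 20** (400,000 draws per cell):

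| z (p) with unlimited imputations | g = 3% | 5% | 10% | 15% | 20% |
|---|---|---|---|---|---|
| 2.1 (0.036) | 0.03% | 0.5% | 4.6% | 10% | 15% |
| 2.0 (0.046) | 17% | 24% | 33% | 38% | 41% |

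The noise also works the other way. At g = 10%, an underlying p of 0.055 is reported below 0.05 for about 28% of seed sets, and 0.06 for about 14%.

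**Patient-level check.** With 15% discontinuation, one simulated dataset had p = 0.0473 at m = 2000. At m = 20 its p-value had a 95% range of 0.034 to 0.063, and 44% of seed sets were not significant.

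**Larger m**, same calculation, g = 10% to 20%:

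| m | z = 2.1 | z = 2.0 |
|---|---|---|
| 20 | 4.6–15% | 33–41% |
| 100 | at most 0.5% | 13–24% |
| 500 | about 0% | 0.5–5% |
| 1000 | about 0% | under 1% |

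**Averaged over all possible results.** The expected z, with pooled variance and 175 per arm, is 0.20/√(2 × 0.40 × 0.60/175) = 3.82 for 50% against 30%, and 0.15/√(2 × 0.375 × 0.625/175) = 2.90 for 45% against 30%. For g = 5% to 20%, the decision with m = 20 differs from that with unlimited imputations in about:

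- 0.3–0.7% of trials at 50% against 30%
- 1.1–2.5% at 45% against 30%
- 0.5–1.1% under the null, where the rejection rate stays at 0.050

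If the expected z is set to match the continuity-corrected power instead, the first two ranges become about 0.4–0.9% and 1.2–2.9%.

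**If the sample size is increased.** Section 14.6 then imputes the interim and post-interim patients independently. The squared weights in the Section 8.7.1 formula sum to 1, so the noise in the combined statistic remains about √(g/20).

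**The case against.** The strongest reply is that nothing here is wrong. Rubin's rules include the finite-m term and a t reference, so the test keeps its 5% level. At 20% missing information the efficiency relative to unlimited imputations is about 99%, and power loss at the design effect is about 0.2 points. The seeds, their order and the extension rule are all pre-committed. At 3–5% missing information a z of 2.1 is hardly affected, and at the design effect a borderline z is itself unlikely. Section 8.1 gives precedence to a statistical analysis plan, not seen here, which may set another number. All of this stands, and it is why the point is minor.

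Stronger readings are tempting but not supported:

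- **Inflated type I error.** The recomputed null rejection rate is 0.050.
- **Room for the sponsor to choose a seed.** Section 14.6 closes that route.
- **Twenty imputations fixed for every secondary endpoint.** The appendix is limited to the primary endpoint. The responder secondaries follow a similar method under Section 8.7.2, and the questionnaire imputation described there states no number.
- **A large effect on the tipping point.** The exposure follows from how that analysis is read, but its size has not been computed. It is run only after a significant primary result and does not decide whether the study is positive.

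What the reply does not answer is that the remaining noise serves no purpose and is cheap to remove.

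**Conclusion.** The point holds as a low-severity matter of precision. The analysis as written is valid and reproducible, but for a result near 0.05 the choice of 20 leaves a material chance that the seed list settles significance. That chance is about 5–15% at z = 2.1 and 33–41% at z = 2.0 for 10–20% missing information, and about 0.03–0.5% and 17–24% for 3–5%. These figures are conditional on a borderline result and on an assumed fraction of missing information. Across all possible results the decision changes in roughly 1% of trials or fewer at the design effect and in about 1–3% at 45% against 30%.

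**What to change.** In Section 14.6, replace 20 with a larger number, for example 500 to 1000, for the primary and sensitivity analyses of the primary endpoint, including the tipping-point analysis. Alternatively, pre-specify a Monte Carlo error limit on the primary p-value and raise the number of imputations until it is met. One hundred would be enough at z = 2.1 but not closer to the cut. Keep the listed seeds and the rule for extending them. If the statistical analysis plan repeats the number, change it there too, before unblinding. The change is one line of text plus computing time, for at most 500 patients; no data collection, model or error rate is affected.
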